11.2.5.2. C-SSRS Suicidal Ideation or Behavior Relative to Pre-Treatment

The number and percentage of subjects with treatment-emergent suicidal ideation or behavior -post-baseline will be presented during the on-treatment and on-study (to Week 52) periods (see Section 9.5.15).

A subject must have at least one pre-treatment C-SSRS assessment (screening and/or baseline) and at least one on-treatment C-SSRS assessment (post-baseline) to be included in this display.

A subject may have treatment emergent suicidal ideation and/or behavior.

The following categories will be presented:

- The number (%) of subjects with any treatment emergent suicidal ideation (1-5)
 - The number (%) of subjects with any treatment emergent more severe suicidal ideation (4-5)
- The number (%) of subjects with any treatment emergent suicidal behavior (6-10)
- The number (%) of subjects with any treatment emergent suicidal ideation (1-5) or suicidal behavior (6-10)

Note: treatment emergent suicidality can only be assessed in subjects with a pre-treatment maximum ideation score of 4 or lower (as subjects with a pre-treatment ideation score of 5 have no potential to worsen on the 1-5 ideation scale)

In addition, a shift table showing the maximum pre-treatment ideation score versus the maximum post-treatment ideation score will be produced for the on-treatment and on-study periods. The maximum pre-treatment behavior score versus the maximum post-treatment behavior score will also be presented in the summary table. These summaries will be provided post Statistical Analysis Complete (SAC).

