9.5.12. Mortality and Protocol-Defined AESI

Mortality status will be derived from the SAE data, where outcome is fatal.

The derivation for the protocol-defined AESIs are provided in the table below. Treatment emergent AESIs (see Section 9.5.13 and Section 9.5.15) only will be summarized.

Where the protocol defined AESI utilize definitions from the PSAP, the detailed derivations from the PSAP are provided in [Appendix 6: PSAP Sections for AESI Reporting](#). AESI are identified per the preferred terms and other criteria described in the PSAP.

Protocol-Defined AESI (see Section 2.2.1 and Section 2.2.3 for clarification)	Definition	Programming Derivation (Protocol Definition)
Serious infections	SAEs within Infections and Infestations SOC.	SOC=Infections and Infestations & AESER = 'Y'
Opportunistic infections and other infections of interest	"All Infections" per PSAP definition to cover all OI and infections of interest.	CQ06NAM ne " or CQ07NAM ne " or CQ08NAM ne "
Non-melanoma skin cancers (NMSC)	NMSC per PSAP definition.	CQ00MLFL = 'Y' and CQ03NAM ne " and CQ03NMFL = 'Y'
Malignancies (excluding NMSC)	PSAP defined, "all malignancies excluding NMSC".	[CQ00MLFL = 'Y' and (CQ01NAM ne " or CQ02NAM ne " or (CQ03NAM ne " and CQ03NMFL ne 'Y'))] Or (CQ04NAM ne " and CQ04NPFL = 'Y')
Psychiatric events suggesting serious mood disorders and anxiety	Serious events from the depression CMQ (PSAP defined – depression including mood disorders and anxiety).	CQ09NAM ne " and AESER = "Y"
Suicidality (C-SSRS)	Any treatment-emergent C-SSRS suicidal ideation (1-5) or suicidal behavior (6-10) (defined in Section 9.5.15) – i.e. maximum ideation score worsens relative to pre-treatment or maximum behavior score worsens relative to pre-treatment	C-SSRS Ideation categories 1-5 and Behavior categories 6-10; any subject with ideation or behavior that is treatment-emergent (defined in Section 9.5.15).
Serious infusion and hypersensitivity reactions	Serious infusion and hypersensitivity reactions per the PSAP definition. Includes all SAEs from the anaphylactic reactions CMQ broad search (see Section 11.2.4, includes events on the day of the infusion or within 3 days after the infusion).	CQ05NAM ne " and AESER='Y' and AEINF3FL='Y'

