9.5.15. Treatment-Emergent C-SSRS

For suicidal ideation, the pre-treatment reference period is the lifetime history, current history and baseline (for further detail refer to the IDSL documentation). For suicidal behavior, the pre-treatment reference period is the lifetime history and baseline (note: suicidal behavior is not re-assessed for the current history time period).

Suicidal ideation and suicidal behavior will be considered as distinct categories and assessed independently of each other. Treatment emergence will be assessed for the on-treatment period and the on-study period.

Suicidal ideation will be assessed using responses to C-SSRS ideation questions (categories 1 to 5) only. Suicidal behavior will be assessed using responses to C-SSRS behavior questions (categories 6 to 10) only.

- **Treatment emergent suicidal ideation** will be assessed using the maximum ideation score pre-treatment, compared to the maximum ideation score post-treatment (on-treatment or on-study as appropriate). If the maximum ideation score worsens relative to the pre-treatment reference period then this will be considered a treatment emergent suicidal ideation. This is derived from responses to suicidal ideation questions (categories 1 to 5).
- **Treatment emergent suicidal behavior** will be assessed using the maximum behavior score pre-treatment, compared to the maximum behavior score post-treatment (on-treatment or on-study as appropriate). If the maximum behavior score worsens relative to the pre-treatment reference period then this will be considered a treatment emergent suicidal behavior. This is derived from responses to suicidal behavior questions (categories 6 to 10).
- **Treatment emergent suicidal ideation or behavior** will be defined as a subject having a treatment emergent suicidal ideation (as defined above) and/or a treatment emergent suicidal behavior (as defined above). This definition is used to assess the protocol defined AESI endpoint of ‘Suicidality (C-SSRS)’ (see Section 9.5.15).

Suicidal Ideation (categories):

1. Wish to be Dead
2. Non-Specific Active Suicidal Thoughts
3. Active Suicidal Ideation with Any Methods (Not Plan) without Intent to Act
4. Active Suicidal Ideation with Some Intent to Act, Without Specific Plan
5. Active Suicidal Ideation with Specific Plan and Intent

Suicidal Behavior (categories):

6. Preparatory Acts or Behavior
7. Aborted Attempt
8. Interrupted Attempt
9. Non-Fatal Actual Suicide Attempt
10. Completed Suicide

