11.1.2. Protocol-Defined AESI

Protocol-defined AESIs are defined in Section [9.5.12](#).

Note, for Suicidality (C-SSRS) only, a subject must have at least one pre-treatment C-SSRS assessment (screening and/or baseline) and at least one on-treatment C-SSRS assessment (post-baseline) to be included in the summaries.

Percentages

For each of the AESIs a summary of the number and percentage of subjects experiencing at least one event will be provided for belimumab and placebo as well as the difference in the percentage of subjects (and 95% CI) between the belimumab and placebo groups using the same methodology as for mortality.

Subject Incidence Rate

The incidence rate for each AESI per 100 subject years will be provided for belimumab and placebo groups as well as the difference between placebo and belimumab (and 95% CI) using the same methodology as for mortality.

Event Incidence Rate

The number of events and event rate for each AESI, except Suicidality (C-SSRS), per 100 subject years will be provided for belimumab and placebo groups.

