A separate summary will present the number and percentage of subjects with worsening at Week 52 compared to baseline by organ domain in treatment completers who have a Week 52 SLICC assessment. Only subjects who have potential to worsen in a given domain will be summarized for that domain, i.e. subjects who do not have the maximum damage score for the domain at baseline.

A summary will also be produced for subjects who complete the study through 52 weeks, i.e. subjects with off-treatment data will be included. The table will display the number and percentage of subjects with worsening in their SLICC/ACR Damage Index score by treatment group and the treatment difference versus placebo.

Subgroups

The SLICC/ACR worsening at Week 52 will be summarized for treatment completers with a Week 52 assessment for subgroups listed in Section 8.3 using the eCRF data to derive randomization stratification factors.

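### The note in Week 52 RAP 11.2.5.2 restricts treatment-emergent suicidality, not just ideation, to pre-treatment ideation of 4 or lower; read literally, it drops worsened-behaviour cases at score 5 from that supplementary display

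*SAP*

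**What the plan says.** Section 11.2.5.2 of the Week 52 RAP describes a display of treatment-emergent C-SSRS results. It has rows for any ideation (1-5), more severe ideation (4-5), any behaviour (6-10), and ideation or behaviour combined. To enter the display a subject needs one pre-treatment and one post-baseline on-treatment assessment. A note then adds that "treatment emergent suicidality can only be assessed in subjects with a pre-treatment maximum ideation score of 4 or lower", giving as its reason "as subjects with a pre-treatment ideation score of 5 have no potential to worsen on the 1-5 ideation scale".

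The definitions are in Section 9.5.15:
- "Suicidal ideation and suicidal behavior will be considered as distinct categories and assessed independently of each other".
- For behaviour: "If the maximum behavior score worsens relative to the pre-treatment reference period then this will be considered a treatment emergent suicidal behavior". No condition on ideation is attached.
- The combined measure is met by either component. Section 9.5.15 says this is the measure used for the protocol-defined AESI Suicidality (C-SSRS).

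Section 9.5.12 derives that AESI as "any subject with ideation or behavior that is treatment-emergent". Section 11.1.2 gives the entry condition for its analysis: "a subject must have at least one pre-treatment C-SSRS assessment (screening and/or baseline) and at least one on-treatment C-SSRS assessment". Neither section mentions a limit on the ideation score.

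**The concern.** The note's wording is wider than its reason. A subject at ideation 5 cannot worsen on ideation, so excluding that subject from the ideation rows is sensible. The same subject can still worsen on behaviour. The highest behaviour category is completed suicide, so no enrolled subject starts at the behaviour ceiling.

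The note nevertheless speaks of suicidality, which is the RAP's name for the combined endpoint. The rows above it say suicidal ideation when ideation alone is meant. A programmer following the note as written would take score-5 subjects out of the behaviour and combined rows as well. The ideation reference period includes lifetime history (9.5.15), so a single past score of 5 would be enough.

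Two things are at stake. The display would leave out worsened behaviour in the subjects with the most severe prior ideation. Its combined row would also use a different numerator and denominator from the same measure in the headline AESI tables, 2.05 (on-treatment) and 2.06 (on-study). Behaviour events are likely to be few, so one omission could change how a row reads.

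**Working it through.** The plan gives no figure on this point to reproduce. The check compares the rules and then counts the score patterns on which they disagree.

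**Inputs**
- Ideation categories 1-5 and behaviour categories 6-10; 0 is used here for none (9.5.15).
- A component is treatment-emergent if its post-treatment maximum exceeds its pre-treatment maximum; the combined measure needs either one (9.5.15).
- Restriction under test: pre-treatment ideation of 4 or lower (note in 11.2.5.2).

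**One subject through each rule.** Take pre-treatment ideation 5, no pre-treatment behaviour, and a non-fatal attempt (category 9) on treatment, with the required assessments present.

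| Rule | Result |
|---|---|
| 9.5.15, behaviour | Event: 0 to 9 is a worsening |
| 9.5.15 and 9.5.12, combined AESI | Event |
| 11.1.2, AESI analysis | Included and counted |
| 11.2.5.2, display's own inclusion rule | Included |
| 11.2.5.2, note read literally | Not assessable in any row |
| 11.2.5.2, note read as ideation only | Event in the behaviour and combined rows |

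**All score patterns.** Pre-treatment ideation takes 6 values (0-5), pre-treatment behaviour 5 (0, 6-9), post-treatment ideation 6 (0-5) and post-treatment behaviour 6 (0, 6-10).

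1. Total patterns: 6 × 5 × 6 × 6 = 1,080.
2. Ideation does not worsen in 1 + 2 + 3 + 4 + 5 + 6 = 21 of the 36 ideation pairs.
3. Behaviour does not worsen in 1 + 2 + 3 + 4 + 5 = 15 of the 30 behaviour pairs, so it worsens in the other 15.
4. Treatment-emergent on the combined measure under 9.5.15: 1,080 − 21 × 15 = 765.
5. Of these, those with pre-treatment ideation 5: ideation cannot worsen, so behaviour must. There are 6 post-treatment ideation values × 15 behaviour worsenings = 90.
6. Treatment-emergent under the literal note: 765 − 90 = 675.
7. Behaviour row alone: 36 × 15 = 540 under 9.5.15, and 540 − 90 = 450 under the literal note.

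All 90 lost patterns are worsened behaviour at pre-treatment ideation 5. Limiting the note to ideation restores all of them and leaves the ideation numerators unchanged. These are counts of logical patterns, not of subjects or risks.

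**What the note does not cause.** If pre-treatment behaviour is already 9, a further non-fatal attempt is not treatment-emergent under 9.5.15, with or without the note. At pre-treatment behaviour of none, 6, 7 or 8, the same attempt is treatment-emergent under 9.5.15.

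**The case against.** The strongest reply is that the note was only ever meant for ideation. Its bracketed reason refers to the ideation scale alone. The same section sets an inclusion rule with no ideation limit, says a subject may have emergent ideation and/or behaviour, gives behaviour its own row, and refers to 9.5.15. On that view one word is loose and nothing is lost. This largely stands as an account of intent. It does not remove the contradiction: the sentence names the combined endpoint, and the separate mock shells that might settle the reading are not among the documents.

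The second reply is about reach, and it stands in full. A reader might infer that a new suicide attempt in a score-5 subject would go uncounted in the trial or in the suicidality AESI. The documents do not support that:
- The AESI definition and analysis (9.5.12, 9.5.15, 11.1.2) carry no ideation limit.
- Section 11.2.5.1 tabulates behaviours regardless of pre-treatment history.
- Section 11.2.5 lists details for every subject with any recorded behaviour.
- Section 11.2.5.2 also plans a pre- versus post-treatment behaviour summary, and 11.2.5.3 a category shift table.
- Protocol Section 7.4 requires an SAE worksheet for any positive behaviour answer.

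A reader might also try to put a number on the events lost. Protocol Section 1.2 gives 180 per 100,000 subject-years for attempts and completed suicide, but in belimumab-treated subjects only. It is not a rate of C-SSRS worsening from lifetime history and gives nothing for placebo. The share of events arising at pre-treatment ideation 5 is not stated anywhere.

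**Conclusion.** The note in 11.2.5.2 is worded more broadly than its own reason and contradicts 9.5.15 and the inclusion rule stated in 9.5.15, 11.1.2 and 11.2.5.2. If followed literally, it removes score-5 subjects with worsened behaviour from the behaviour and combined rows of one supplementary display. In pattern terms that is 90 of the 765 combinations that count under 9.5.15, all of them behaviour worsenings. The number of subjects cannot be quantified from the documents.

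The mismatch with Tables 2.05 and 2.06 is conditional: it arises only if the literal reading is programmed and at least one score-5 subject is otherwise eligible for the display. The denominator of the combined row would then differ, and the numerator too if any such subject's behaviour worsened. This is an inconsistency worth correcting in a named safety endpoint. It is not a defect in the protocol-defined AESI analysis.

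**What to change.** In the note, replace *suicidality* with *suicidal ideation*, so that the limit of 4 or lower applies to treatment-emergent ideation only. Add that subjects with a pre-treatment score of 5 remain evaluable in the behaviour and combined rows, and count there if their behaviour score worsens. Restrict the denominator to scores of 4 or lower for the two ideation rows only, and state each row's denominator. The RAP already takes this component-by-component approach for organ damage in 12.2.3.2: "Only subjects who have potential to worsen in a given domain will be summarized for that domain". Leave the AESI definition behind Tables 2.05 and 2.06 as it is.

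The cost is a wording change and one denominator flag, with no new data. The Years 2 to 5 RAP records that the Week 52 analysis was completed on 7-FEB-2019. For that reported analysis, the equivalent step is to confirm which reading was programmed and, if it was the literal one, reissue this display.

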11.2.5.3. C-SSRS Shift Changes in Categories from Pre-Treatment to On-Treatment

A summary of the shift from maximum pre-treatment C-SSRS category to maximum on-treatment and on-study (to Week 52) category will be produced.

The pre-treatment period for ideation is based on the lifetime, current and baseline history. For behavior, it is based on the lifetime and baseline history. A subject must have at least one pre-treatment assessment and at least one on-study assessment to be included in this display.

The table will display the number and percentage of subjects within the specific shift categories: No suicidal ideation or behavior, suicidal ideation, and suicidal behavior.

Each subject will appear in the table only once. For the purposes of this table only, a subject with both suicidal ideation and suicidal behavior in any period (pre-treatment/on-treatment/on-study) will appear in the category of suicidal behavior only.

12. EFFICACY ANALYSES

The efficacy analyses will be performed for the ITT population as defined in Section 6 unless otherwise stated. The data will be presented by treatment group.

12.1. Major Efficacy Analyses

12.1.1. Percent of Subjects with Prednisone Reduction by $\geq 25\%$ from baseline to ≤ 7.5 mg/day during Week 40 through Week 52

Primary Analysis

For this analysis, only steroids used to treat SLE will be included and only subjects with a baseline average daily prednisone dose >7.5 mg/day will be included. See Section 9.5.16.1 for derivation of baseline prednisone dose and Section 9.5.16.2 for derivation of average prednisone use between Week 40 to Week 52.

The percent of subjects whose average prednisone dose has been reduced by $\geq 25\%$ from baseline to ≤ 7.5 mg/day during Weeks 40 through 52 will be compared between belimumab and placebo using a logistic regression model. Independent variables in the model will include treatment group, baseline prednisone dose, and the following

randomization stratification factors per the eCRF: screening SELENA SLEDAI score (≤ 9 vs. ≥ 10), and region. A responder is defined as having a prednisone reduction by $\geq 25\%$ from baseline to ≤ 7.5 mg/day during Weeks 40 through 52.

Any subject who withdraws from the study or adds new immunomodulatory agents used to treat SLE (note that this will include switches) prior to the Week 52 visit will be considered having no steroid reduction.

A summary of the number and percentage of subjects who are responders by treatment group, the treatment difference versus placebo, the odds ratio and 95% CI versus placebo, and a p-value for the odds ratio will also be provided.

Sensitivity Analysis

- To examine the robustness of the results, a sensitivity analysis of the SLE-related steroid reduction will be performed without considering any information related to the use of new immunomodulatory agents (note that this will include switches).

Additional Summaries of Prednisone

- A summary of the number and percentage of subjects with average SLE-related daily prednisone dose ≤ 7.5 mg/day and > 7.5 mg/day at baseline (Day 1) and treatment completion date will be presented for treatment completers.
- The cumulative SLE-related prednisone dose will be derived as described in Section 9.5.16.3. A table of descriptive statistics will be presented including the mean, standard deviation, median, 25th and 75th percentiles, minimum and maximum.
- A listing of cumulative SLE-related prednisone dose will be displayed by treatment and subject.

